7.2.5 Volume of Blood to Be Drawn From Each Subject

Table 9 Approximate Volume of Blood to Be Drawn From Each Subject

Assessment		Sample Volume (mL)	Number of Samples	Total Volume (mL)
PK/PD		7	20 ^b	140
Immunogenicity (anti-C1 INH antibodies)		5	13	65
Safety	Biochemistry and β-HCG ^a	6	13	78
	Hematology	2	13	26
	Coagulation	3	13	39
Virology		6	1	6
All assessments (mL)				354

B-hCG=beta human chorionic gonadotrophin; C1 INH=C1 inhibitor; PD=pharmacodynamics; PK=pharmacokinetics

^aβ-hCG testing for females of childbearing potential at the Visit 1a (predose) only.

^bTwo of the 20 samples are optional as indicated in [Table 4](#).

During this study, it is expected that maximum volume of blood to be drawn from each subject will be 354 mL, as shown in [Table 9](#).

Note: The amount of blood to be drawn for each assessment is an estimate. The amount of blood drawn may vary according to the instructions provided by the manufacturer or laboratory for an individual assessment; however, the total volume drawn over the course of the study should be approximately 354 mL. When more than 1 blood assessment is done at the same time point/period, if they require the same type of tube, the assessments may be combined.

8. ADVERSE AND SERIOUS ADVERSE EVENTS ASSESSMENT

8.1 Definition of Adverse Events, Period of Observation, Recording of Adverse Events

An **AE** is any untoward medical occurrence in a clinical investigation subject administered a pharmaceutical product and that does not necessarily have a causal relationship with this treatment. An AE can therefore be any unfavorable and unintended sign (including an abnormal laboratory finding), symptom, or disease temporally associated with the use of a medicinal (investigational) product, whether or not related to the medicinal (investigational) product (ICH Guidance E2A 1995).

All AEs are collected from the time the informed consent is signed until 7 days after the last dose of investigational product. This includes events occurring during the screening phase of the study, regardless of whether or not investigational product is administered. Where possible, a diagnosis rather than a list of symptoms should be recorded. If a diagnosis has not been made, then each symptom should be listed individually. All AEs should be captured on the appropriate AE pages in the CRF and in source documents. In addition to untoward AEs, unexpected benefits outside the investigational product indication should also be captured on the AE CRF.

All AEs must be followed to closure (the subject's health has returned to his/her baseline status or all variables have returned to normal), regardless of whether the subject is still participating in the study. Closure indicates that an outcome is reached, stabilization achieved (the investigator does not expect any further improvement or worsening of the event), or the event is otherwise explained. When appropriate, medical tests and examinations are performed so that resolution of event(s) can be documented.

8.1.1 Severity Categorization

The severity of AEs must be recorded during the course of the event including the start and stop dates for each change in severity. An event that changes in severity should be captured as a new event. Worsening of pretreatment events, after initiation of investigational product, must be recorded as new AEs (for example, if a subject experiences mild intermittent dyspepsia prior to dosing of investigational product, but the dyspepsia becomes severe and more frequent after first dose of investigational product has been administered, a new AE of severe dyspepsia [with the appropriate date of onset] is recorded on the appropriate CRF).

The medical assessment of severity is determined by using the following definitions:

Mild: A type of AE that is usually transient and may require only minimal treatment or therapeutic intervention. The event does not generally interfere with usual activities of daily living.

Moderate: A type of AE that is usually alleviated with specific therapeutic intervention. The event interferes with usual activities of daily living, causing discomfort but poses no significant or permanent risk of harm to the research subject.

Severe: A type of AE that interrupts usual activities of daily living, or significantly affects clinical status, or may require intensive therapeutic intervention.

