11. SAFETY ANALYSES

The safety analyses will be performed by treatment using the Safety Set. Safety endpoints include adverse events (AE), clinical laboratory assessments, vital signs, ECG findings, SC injection site reactions, C1 INH antibody status and patient-reported tolerability of icatibant therapy for acute angioedema attacks. The last assessment prior to the first dose of investigational product in treatment period 1 will be used as baseline for all safety analyses.

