11.1 Adverse Events

Adverse events will be coded using the Medical Dictionary for Regulatory Activities (MedDRA), Version 19.0 adverse events dictionary.

Adverse events will be collected from the time of informed consent through 7 days after the last dose date of investigational product. All serious adverse events (SAE) that occur \leq 30 days after the last dose date of investigational product and related SAEs that occur >30 days after the last dose date of investigational product will be collected.

An adverse event that increases in severity will be captured as a new event. An AE that develops into a SAE will be captured as a new event from the date it met the seriousness criteria. Worsening of pre-treatment events, after initiation of investigational product, will be recorded as new AE. An AE (classified by preferred term) that occurs during the study will be considered a treatment emergent adverse event (TEAE) if the start date and time of the AE is on or after the first dose date of investigational product and up to 7 days after the last dose of investigational product and up to 30 days after the last dose of investigational product, or with an increase in severity on or after the date and time of the first dose.

In addition, angioedema attacks and ISRs will not be considered AEs unless they satisfy serious criteria according to the protocol.

The number and percentage of subjects reporting any TEAEs, SAEs, and TEAEs related to investigational product, TEAEs leading to withdrawal, Severe TEAEs and absolute count of events will be summarized. Angioedema attacks and ISRs will not be considered AEs unless they satisfy serious criteria according to the protocol.

The number and percentage of subjects reporting any TEAEs, and absolute count of events will also be summarized in the following ways:

- By SOC, preferred term and treatment
- By SOC, preferred term, treatment and maximum severity
- By SOC, preferred term, treatment and relationship to investigational product in the opinion of the investigator
- By preferred term

TEAEs leading to withdrawal, SAEs, and deaths will be similarly summarized as TEAEs.

CONFIDENTIAL

Shire SHP616-300 Statistical Analysis Plan idursulfase IT

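### The protocol makes every change in AE severity a new event, the SAP mentions only increases, and nothing stops an easing AE from being counted as a new TEAE

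*Protocol*

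**What the plan says.** Protocol 8.1.1 gives a general recording rule: "An event that changes in severity should be captured as a new event". It also requires the dates: "The severity of AEs must be recorded during the course of the event including the start and stop dates for each change in severity". A separate sentence deals with events present before dosing: "Worsening of pretreatment events, after initiation of investigational product, must be recorded as new AEs".

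SAP 11.1 restates the recording rule more narrowly: "An adverse event that increases in severity will be captured as a new event". Decreases are not mentioned. The TEAE definition then has two alternatives. The first is met "if the start date and time of the AE is on or after the first dose date of investigational product", within the follow-up window. The second is met by an AE "or with an increase in severity on or after the date and time of the first dose". SAP 16 declares no changes from the protocol, so the narrower wording is not presented as a deliberate departure.

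On output, SAP 11 states: "The safety analyses will be performed by treatment using the Safety Set". SAP 11.1 adds: "The number and percentage of subjects reporting any TEAEs, and absolute count of events will also be summarized in the following ways". Subject counts, percentages and event counts are therefore all affected by how a record is defined.

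**The concern.** Sites follow the protocol. An AE that eases from moderate to mild should therefore produce a second record with its own start date. The SAP's start-date test does not ask whether severity rose or fell, and no SAP text links the second record to the first. A resolving event can then be tabulated as a new treatment-emergent one.

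The design gives this two places to matter beyond event counts. AEs are collected from consent, so one can be present before first dose and ease afterwards. The periods also run on without a washout, so an AE can begin on one treatment and ease on the other. At stake is the by-treatment TEAE comparison, a core safety output, which would depend on which document the programmer follows. No efficacy result, sample size or alpha level is involved.

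**Working it through.** The plan gives no figure to reproduce here, so the check applies the two recording rules to the same event histories.

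Inputs:
- Protocol recording: a new record at any severity change (Protocol 8.1.1).
- SAP recording: a new record at an increase only, the natural reading of SAP 11.1.
- TEAE test: record starts on or after first dose, within the follow-up window (SAP 11.1).
- Period 2 begins on day 99, because 14 weeks × 7 = 98 days per period and there is no washout (Protocol 3.1).
- Treatment attribution: the period in which the record starts. The SAP does not state this. It is inferred from the by-treatment summaries and from SAP 11.1 moving early Period 2 TEAEs back to Period 1 only as a sensitivity analysis.

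TEAE records, protocol recording against SAP recording:
- Moderate at screening, mild on day 5: 1 against 0.
- Moderate on day 90, mild on day 101: 2 (one in each period) against 1 (Period 1 only).
- Severe on day 20, moderate on day 24, mild on day 28: 3 against 1, all in Period 1.
- Mild at screening, severe on day 5: 1 against 1.

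The rules differ only when an AE improves. In the third history the subject is already a TEAE subject and maximum severity stays severe, so only the event count changes. Subject incidence can change only in the first two histories, where the AE spans first dose or the crossover.

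For size, the documents give no rate of AEs ongoing at the crossover, so a range is assumed. The planned A/B group is 26 subjects. The placebo column pools A/B and B/A (SAP 17.1), so its planned size is 26 + 26 = 52.
- At 5%: 0.05 × 26 = 1.3 subjects; 1.3 / 52 = 2.5 percentage points.
- At 20%: 0.20 × 26 = 5.2 subjects; 5.2 / 52 = 10 percentage points.

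These are ceilings for overall placebo TEAE incidence, because a subject with any other placebo TEAE is already counted.

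**The case against.** The SAP does not say that only increases count; it is silent on decreases. That is correct, and the point is a mismatch and a missing rule, not two rules in outright contradiction.

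The pretreatment case is open to dispute. Protocol 8.1.1 has its own sentence on worsening of pretreatment events, and a site could take it as the governing rule and open no new record when a screening AE eases. This stands as a reason to hold that case less firmly. It does not touch the crossover case or the within-period event counts.

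The TEAE test could be read as referring to the first onset of the event, since otherwise its increase alternative would add nothing. This does not settle the matter. Under the SAP's own recording sentence, an increase after first dose is already a new event with a post-dose start, so that alternative is redundant either way.

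SAP 11.1 has two sensitivity analyses for the opening two weeks of Period 2: one reassigns A/B TEAEs to Period 1, the other drops all TEAEs in that window. The day-101 example falls within it (days 99 to 112), so part of the problem is examined. But neither analysis separates improvement records from true onsets. Neither reaches records from day 113 onward, screening AEs or event counts within Period 1.

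Finally, non-serious injection site reactions and angioedema attacks are not AEs, which removes an expected source of records. The CRF layout, data management plan and table specifications are not available and might collapse such records. Both facts limit the likely size; neither supplies the missing rule.

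**Conclusion.** The point holds. Following both documents as written counts an AE that only improves as a new TEAE. Within a period this inflates event counts alone. Across the crossover it can add a TEAE subject on the other treatment, provided TEAEs are attributed to the current period, which is inferred. Across first dose it can do the same, with less certainty.

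A reader might infer that this systematically shrinks the active-placebo safety difference, because in A/B resolving active-period AEs appear under placebo. The documents do not support that as a general statement. B/A has the same planned size, and there resolving placebo AEs appear under active. The net sign depends on the two flows; the treatments are pulled together only if active causes more AEs.

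A reader might also express the effect as a share of the 26 A/B subjects. The planned placebo column is about 52, which gives the ceiling of 2.5 to 10 percentage points. That range rests wholly on the assumed 5% to 20%; the true size cannot be derived from the documents.

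**What to change.** In SAP 11.1, add three statements:
- Contiguous records of the same event are linked as one AE.
- Only a first onset or an increase in severity on or after first dose, within the existing window, counts as a TEAE; a decrease is not a new event.
- Each TEAE is assigned to the treatment being received at the date of that onset or increase.

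The protocol can keep recording dated severity changes, which are useful data, but the recording sentences in Protocol 8.1.1 and SAP 11.1 should be reconciled so that both say when a record is a new event.

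The cost is a few sentences and one derivation from event terms and the severity dates that the protocol already requires. No new data are needed.

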8.1.2 Relationship Categorization

A physician/investigator must make the assessment of relationship to investigational product for each AE. The investigator should decide whether, in his or her medical judgment, there is a reasonable possibility that the event may have been caused by the investigational product. If there is no valid reason for suggesting a relationship, then the AE should be classified as “not related.” Otherwise, if there is any valid reason, even if undetermined or untested, for suspecting a possible cause-and-effect relationship between the investigational product and the occurrence of the AE, then the AE should be considered “related.” The causality assessment must be documented in the source document.

The following additional guidance may be helpful:

Term	Relationship Definition
Related	The temporal relationship between the event and the administration of the investigational product and/or other study product (eg, icatibant) is compelling and/or follows a known or suspected response pattern to that product, and the event cannot be explained by the subject's medical condition, other therapies, or accident.
Not Related	The event can be readily explained by other factors such as the subject's underlying medical condition, concomitant therapy, or accident and no plausible temporal or biologic relationship exists between the investigational product and/or other study product (eg, icatibant) and the event.

8.1.3 Outcome Categorization

The outcome of AEs must be recorded during the course of the study on the CRF. Outcomes are as follows:

- Fatal
- Not Recovered/Not Resolved
- Recovered/Resolved
- Recovered/Resolved With Sequelae
- Recovering/Resolving

- Unknown

8.1.4 Symptoms of the Disease Under Study

Symptoms of the disease under study (angioedema attacks) should not be captured as AEs as long as they are within the normal day-to-day fluctuation or expected progression of the disease and are part of the efficacy data to be collected in the study; however, events satisfying the serious criteria should be recorded as a SAE and reported to Shire Pharmacovigilance.

8.1.5 Clinical Laboratory and Other Safety Evaluations

A change in the value of a clinical laboratory, vital sign, or ECG assessment can represent an AE if the change is clinically relevant or if, during treatment with the investigational product, a shift of a parameter is observed from a normal value to an abnormal value, or a further worsening of an already abnormal value. When evaluating such changes, the extent of deviation from the reference range, the duration until return to the reference range (either while continuing treatment or after the end of treatment with the investigational product), and the range of variation of the respective parameter within its reference range must be taken into consideration.

If, at the end of the treatment phase, there are abnormal clinical laboratory, vital sign, or ECG values which were not present at the pretreatment value observed closest to the start of study treatment, further investigations should be performed until the values return to within the reference range or until a plausible explanation (eg, concomitant disease) is found for the abnormal values.

The investigator should decide, based on the above criteria and the clinical condition of a subject, whether a change in a clinical laboratory, vital sign, or ECG parameter is clinically significant and therefore represents an AE.

8.1.6 Pregnancy

All pregnancies are to be reported from the time informed consent is signed until the defined follow-up period stated in Section [7.1.5](#).

Any report of pregnancy for any female study participant or the partner of a male study participant must be reported within 24 hours to the Shire Pharmacovigilance Department using the Shire Investigational and Marketed Products Pregnancy Report Form. A copy of the Shire Investigational and Marketed Products Pregnancy Report Form (and any applicable follow-up reports) must also be sent to the CRO/Shire ViroPharma Medical Monitor using the details specified in the emergency contact information section of the protocol. The pregnant female study participant must be withdrawn from the study.

Every effort should be made to gather information regarding the pregnancy outcome and condition of the infant. It is the responsibility of the investigator to obtain this information within 30 calendar days after the initial notification and approximately 30 calendar days postpartum.

Pregnancy complications such as spontaneous abortion/miscarriage or congenital abnormality are considered SAEs and must be reported to Global Pharmacovigilance using the Shire Clinical Trial Serious Adverse Event Form. Note: An elective abortion is not considered an SAE.

In addition to the above, if the investigator determines that the pregnancy meets serious criteria, it must be reported as an SAE using the Shire Clinical Trial Serious Adverse Event Form as well as the Shire Investigational and Marketed Products Pregnancy Report Form. The test date of the first positive serum/urine β -hCG test or ultrasound result will determine the pregnancy onset date.

8.1.7 Abuse, Misuse, Overdose, and Medication Error

Abuse, misuse, overdose, or medication error (as defined below) must be reported to the sponsor according to the SAE reporting procedure whether or not they result in an AE/SAE as described in Section 8.2. Note: The 24-hour reporting requirement for SAEs does not apply to reports of abuse, misuse, overdose, or medication errors unless these result in an SAE.

The categories below are not mutually exclusive; the event can meet more than 1 category.

- **Abuse** – Persistent or sporadic intentional intake of investigational product when used for a non-medical purpose (eg, to alter one's state of consciousness or get high) in a manner that may be detrimental to the individual and/or society.
- **Misuse** – Intentional use of investigational product other than as directed or indicated at any dose (Note: This includes a situation where the investigational product is not used as directed at the dose prescribed by the protocol).
- **Overdose** – Intentional or unintentional intake of a dose of an investigational product higher than the protocol-specified dose.
- **Medication Error** – An error made in prescribing, dispensing, administration, and/or use of an investigational product. For studies, medication errors are reportable to the sponsor only as defined below.

Medication errors should be collected and reported to the sponsor for all products under investigation. The following should be considered as examples of reportable medication errors:

- The administration and/or use of the unassigned treatment
- The administration and/or use of an expired investigational product
- Violation of storage or refrigeration requirements for the investigational product

Cases of subjects missing doses of the investigational product are not considered reportable as medication errors.

All investigational products administered to pediatric subjects should be supervised by the parent/legally authorized representative/caregiver.

8.1.8 Adverse Events of Special Interest

In addition, the following adverse events of special interest will be closely monitored and reported throughout the study, regardless of relationship to study medication:

- Any serious anaphylactic reaction (see Section 4.4.3).

- Any serious thrombotic or thromboembolic event; stopping rules related to thrombotic or thromboembolic events are described in Section 4.4.4.

8.2 Serious Adverse Event Procedures

8.2.1 Reference Safety Information

The reference for safety information for this study is the CINRYZE Investigator's Brochure, which the sponsor has provided under separate cover to all investigators.

8.2.2 Reporting Procedures

All initial and follow-up SAE reports must be reported by the investigator to the Shire Pharmacovigilance Department within 24 hours of the first awareness of the event. Note: The 24-hour reporting requirement for SAEs does not apply to reports of abuse, misuse, overdose, or medication errors (Section 8.1.7) unless they result in an SAE.

The investigator must complete, sign, and date the Shire Clinical Trial Serious Adverse Event Form and verify the accuracy of the information recorded on the form with the corresponding source documents (Note: Source documents are not to be sent unless requested) and fax or e-mail the form to the Shire Pharmacovigilance Department. A copy of the Shire Clinical Trial Serious Adverse Event Form (and any applicable follow-up reports) must also be sent to the contract research organization (CRO)/Shire ViroPharma Medical Monitor using the details specified in the emergency contact information section of the protocol.

8.2.3 Serious Adverse Event Definition

A **Serious Adverse Event (SAE)** is any untoward medical occurrence (whether considered to be related to investigational product or not) that at any dose:

- Results in death.
- Is life-threatening. Note: The term "life-threatening" in the definition of "serious" refers to an event in which the subject was at risk of death at the time of the event; it does not refer to an event which hypothetically might have caused death if it was more severe.
- Requires inpatient hospitalization or prolongation of existing hospitalization. Note: Hospitalizations, which are the result of elective or previously scheduled surgery for pre-existing conditions that have not worsened after initiation of treatment, should not be classified as SAEs. For example, an admission for a previously scheduled ventral hernia repair would not be classified as an SAE; however, complication(s) resulting from a hospitalization for an elective or previously scheduled surgery that meet(s) serious criteria must be reported as an SAE(s).
- Results in persistent or significant disability/incapacity.
- Is a congenital abnormality/birth defect.
- Is an important medical event. Note: Important medical events that may not result in death, be life-threatening, or require hospitalization may be considered an SAE when, based upon appropriate medical judgment, they may jeopardize the subject and may require medical or

surgical intervention to prevent 1 of the outcomes listed in this definition. Examples of such medical events include allergic bronchospasm requiring intensive treatment in an emergency room or at home, blood dyscrasias or convulsions that do not result in inpatient hospitalization, or the development of drug dependency or drug abuse.

